APPENDIX F. PROTOCOL AMENDMENT SUMMARY OF CHANGES

| Document | Date |
|------------------------|-------------|
| Amendment (Version) 1: | 17 MAY 2017 |
| Amendment (Version) 2: | 08 JAN 2018 |
| Amendment (Version) 3: | 01 AUG 2019 |

Amendment 3 (01 AUG 2019)

Overall Rationale for the Amendment: The primary purpose of this amendment is to increase the length of the open-label extension period from 52 weeks to 104 weeks and the follow-up period from 3 months to 6 months.

1. **Synopsis; Section 1.7, Study Rationale and Justification of Dose; Section 4.1, Overall Study Design (including Figure 1: Study Design Schema); Section 4.4, Duration of Treatment and Subject Participation; Section 6, Study Assessments; Section 6.3, Treatment; Section 6.4, Follow-Up; Section 7.5.4, Electrocardiograms; Section 7.5.5.3, Urinalysis**

Description of changes: The length of the open-label extension period was changed from 52 weeks to 104 weeks, with visits added approximately every 12 weeks during the extension period. The length of the follow-up period was changed from 3 months to 6 months. Assessments and the description of the duration of the study were updated accordingly as appropriate.

Rationale for change: The durations of the open-label extension and follow-up periods were increased to gather information [REDACTED] and maintenance of response data as well as longer-term safety information.

2. **Synopsis; Section 4.1, Overall Study Design; Section 5.4.1, Dose Modifications; Section 5.4.4, Criteria and Procedures for Dose Increases of Study Drug; Section 7.6.4, Physician's Global Vitiligo Assessment**

Description of changes: Language was updated to permit dose modifications after Week 80 for subjects who have complete facial repigmentation that is first observed after Week 80.

Rationale for change: Since the study treatment duration has increased by an additional 52 weeks, this allows for possible modification of the dosing at additional timepoints during treatment.

3. **Incorporation of administrative changes.** Other minor, administrative changes have been incorporated throughout the Protocol and are noted in the redline version of the amendment.

Amendment 2 (08 JAN 2018)

Overall Rationale for the Amendment:

The primary purpose of this amendment is to remove the enrollment cap for subjects over 30 years of age.

1. Synopsis, Overall Study Design; Section 4.1, Overall Study Design; Section 5.1.2, Randomization and Blinding

Description of changes: Removed the enrollment cap for subjects over 30 years of age.

Rationale for change: Original enrollment cap (no more than 50% of subjects) for subjects over 30 years of age is not operationally feasible and would limit the ability to deliver study results within a reasonable timeframe.

2. Section 7.6.1, Vitiligo Area and Severity Index

Description of changes: Updated F-VASI and hand unit definition.

Rationale for change: To further clarify the definition of face area and VASI measurement.

3. Section 4.1, Overall Study Design; Section 5.1.2, Randomization and Blinding; Section 6.3, Treatment

Description of changes: Revised text so that the members of the primary endpoint assessment team from Incyte will be unblinded at Week 24.

Rationale for change: To facilitate future clinical study planning.

4. Incorporation of administrative changes. Other minor, administrative changes have been incorporated throughout the Protocol and are noted in the redline version of the amendment.

Amendment 1 (17 MAY 2017)

Overall Rationale for the Amendment:

The primary purpose of this amendment is to remove enrollment of subjects aged 12 to 17 years, and update the enrollment cap for subjects over 30 years of age to no more than 50% of subjects.

This amendment includes the changes to the Protocol INCB 18424-211 (20 JAN 2017) summarized below. A redline version of the amendment depicting the updated and previous text is also provided.

- 1. Synopsis, Overall Study Design, Study Population, Key Inclusion Criteria; Section 1.7, Study Rationale and Justification of Dose; Section 3.1, Subject Inclusion Criteria; Section 4.1, Overall Study Design (Figure 1); Section 5.1.2, Randomization and Blinding**

Description of changes: Removed subjects aged 12 to 17 years.

Rationale for change: Study population was changed in consideration of FDA concerns that there is insufficient information from nonclinical juvenile toxicity studies at this time to assess risks in pediatric subjects.

- 2. Synopsis, Overall Study Design; Section 4.1, Overall Study Design; Section 5.1.2, Randomization and Blinding**

Description of changes: Updated enrollment cap for subjects over 30 years of age to no more than 50% of subjects.

Rationale for change: To ensure a disease-appropriate age distribution for enrolled subjects.

- 3. Section 7.6.3, Vitiligo European Task Force Scale; Appendix D, Vitiligo European Task Force Scale**

Description of changes: Updated stage of disease (staging) in the Vitiligo European Task Force (VETF) Scale.

Rationale for change: To make Section 7.6.3 and Appendix D consistent.

- 4. Section 2.2.2, Other Secondary Endpoints; Section 9.3.2 Secondary Analysis; Section 9.4.1.3 Secondary Efficacy Analyses; Section 9.4.2.2 Clinical Laboratory Tests; 9.4.2.4 Electrocardiograms.**

Description of changes: Corrected and updated analysis language. Shortened the Clinical Laboratory Tests section and removed the Electrocardiograms section.

Rationale for change: To update statistical analysis language as some sections (eg, Clinical Laboratory Tests) are not applicable for a topical INCB018424 study.

[REDACTED]

[REDACTED]

[REDACTED]

[REDACTED]

6. **Incorporation of administrative changes.** Other minor, administrative changes have been incorporated throughout the Protocol and are noted in the redline version of the amendment.

## LIST OF ABBREVIATIONS

Abbreviation	Term
AE	adverse event
BID	twice daily
BMI	body mass index
BSA	body surface area
CRF	case report form
CTCAE	Common Terminology Criteria for Adverse Events
DB	double-blind
ECG	electrocardiogram
eCRF	electronic case report form
F-BSA	facial body surface area
F-PaGVA	facial assessment of the Patient's Global Vitiligo Assessment
F-PhGVA	facial assessment of the Physician's Global Vitiligo Assessment
F-VASI	facial assessment of the Vitiligo Area and Severity Index
ITT	intent-to-treat
MedDRA	Medical Dictionary for Regulatory Activities
NCI	National Cancer Institute
NRI	nonresponder imputation
OL	open-label
PaGIC-V	Patient Global Impression of Change for Vitiligo
palmar method of BSA assessment	1% BSA for each subject is approximately equal to the surface area of their palm plus 5 digits; handprint may be used interchangeably
PP	per protocol
PT	preferred term
QD	once daily
SAE	serious adverse event
SAP	statistical analysis plan
SOC	system organ class

T-BSA	total body surface area	
TEAE	treatment-emergent adverse event	
T-PaGVA	total body assessment of the Patient's Global Vitiligo Assessment	

Abbreviation	Term
T-PhGVA	total body assessment of the Physician's Global Vitiligo Assessment
T-VASI	total body assessment of Vitiligo Area and Severity Index
VASI	Vitiligo Area and Severity Index
VASI50	≥ 50% improvement from baseline in Vitiligo Area and Severity Index score
VASI75	≥ 75% improvement from baseline in Vitiligo Area and Severity Index score
VASI90	≥ 90% improvement from baseline in Vitiligo Area and Severity Index score
VETF	Vitiligo European Task Force
WHO	World Health Organization

#### 1. INTRODUCTION

This is a randomized and vehicle-controlled study in subjects with vitiligo who have depigmented areas including at least 0.5% of the T-BSA on the face and at least 3% of the T-BSA on nonfacial areas. The study will consist of 3 parts, including a 24-week, DB, vehiclecontrolled treatment period; a 28-week, continued, DB treatment period; and a 52-week, OL extension period. Section 1 of the Protocol provides a detailed description of the investigational product, target patient population, rationale for doses to be examined, and potential risks and benefits of treatment with INCB018424 cream.

The purpose of this SAP is to provide details of the statistical analyses that have been outlined in the Study INCB 18424-211 Protocol. The scope of this plan includes the interim and final analyses that are planned and will be executed by the Department of Biostatistics or designee

#### 2. STUDY INFORMATION, OBJECTIVES, AND ENDPOINTS

#### 2.1. Protocol and Case Report Form Version

This SAP is based on INCB 18424-211 Protocol Amendment 1 dated 17 MAY 2017 and CRFs approved 06 JUN 2017. Unless superseded by an amendment, this SAP will be effective for all subsequent Protocol amendments and eCRF versions.

## 2.2. Study Objectives

### 2.2.1. Primary Objective

• To establish the efficacy of 24 weeks of treatment with INCB018424 cream in subjects with vitiligo.

#### 2.2.2. Secondary Objectives

- To estimate the dose-response relationship of INCB018424 cream at Weeks 24 and 52.
- To evaluate the safety and tolerability of INCB018424 cream in subjects with vitiligo.

## 2.3. Study Endpoints

#### 2.3.1. Primary Endpoint

Proportion of subjects treated with INCB018424 cream who achieve a ≥ 50% improvement from baseline in F-VASI score (F-VASI50) at Week 24 compared with subjects treated with vehicle cream.

#### 2.3.2. Secondary Endpoints

[figure not shown]
#### 2.3.2.1. Key Secondary Endpoints

- Proportion of subjects who achieve an F-PhGVA of clear or almost clear at Week 24.
- Proportion of subjects who achieve a ≥ 50% improvement from baseline in T-VASI at Week 52.

#### 2.3.2.2. Other Secondary Endpoints

- Assessment of the dose response on percentage change from baseline in F-VASI during the treatment periods.
- Mean and percentage change from baseline in F-VASI score during the treatment periods.
- Proportion of subjects who achieve an F-VASI50 during the treatment periods.
- Percentage change from baseline in F-BSA repigmentation during the treatment periods.
- Percentage change from baseline in T-BSA repigmentation during the treatment periods.
- Mean and percentage change from baseline in T-VASI score during the treatment periods.
- Mean and percentage change from baseline in VETF during the treatment periods.
- Proportion of subjects in each F-PhGVA and T-PhGVA category during the treatment periods.
- Proportion of subjects in each F-PaGVA and T-PaGVA category during the treatment periods.
- Proportions of subjects in each PaGIC-V category during the treatment periods.
- Proportion of subjects who report PaGIC-V of very much improved or much improved during the treatment periods.
- Times to achieve an F-VASI50 and T-VASI50.

- Times to achieve an F-PhGVA and T-PhGVA of clear or almost clear.
- Time to achieve a PaGIC-V of very much improved or much improved.
- Safety and tolerability assessed by monitoring the frequency, duration, and severity of AEs, physical examination, vital signs, and laboratory data for hematology, serum chemistry, and urinalysis.

#### 3. STUDY DESIGN

This is a 3-part, randomized, DB, and vehicle-controlled study in subjects with vitiligo who have depigmented areas including at least 0.5% of the T-BSA on the face and at least 3% of the T-BSA on nonfacial areas as determined by the palmar (or handprint- palm plus 5 digits) method. Approximately 150 subjects, aged 18 to 75 years, will be randomized to 1 of 4 dose strengths of INCB018424 cream (1.5% BID, 1.5% QD, 0.5% QD, 0.15% QD) or vehicle cream in a 1:1:1:1:1 ratio and stratified by age ( $\leq$  30 or > 30 years), with no more than 50% of the population being over 30 years of age.

Subjects will receive blinded treatment for up to 52 weeks to examine efficacy, safety, and tolerability. The 3 parts of the study include a 24-week, DB, vehicle-controlled treatment period; a 28-week, continued, DB treatment period; and a 52-week, OL extension period (see Figure 1). The primary endpoint of F-VASI50 will be evaluated at Week 24. After completion of the Week 24 assessments, subjects randomized to vehicle will be randomized to 1 of the 3 higher active treatment groups in a 1:1:1 ratio while maintaining the blind. Subjects in the INCB018424 0.15% QD group who do not achieve a  $\geq$  25% improvement from baseline on F-VASI (nonresponders of F-VASI25) will be re-randomized to 1 of the 3 higher active treatment groups while maintaining the blind. Subjects randomized to INCB018424 0.15% QD who achieve a  $\geq$  25% improvement from baseline on F-VASI will remain on the same dose until Week 52. Subjects randomized to INCB018424 1.5% BID, 1.5% QD, and 0.5% QD will remain on the same dose until Week 52.

After completion of the Week 52 assessments, subjects who continue to be eligible for the study have the opportunity to receive an additional 52 weeks of OL treatment with INCB018424 1.5% cream BID.

Figure 1: Study Design Schema

Screening		Double-Blind (		Open-Label	Follow-up
Up to 28 days		Day 1 to Week 24 a	Weeks 24 to 52	Weeks 52 to 104 b	Up to 97 days
Men and women aged 18 to 75 years with vitiligo ≥ 0.5% facial BSA and ≥ 3% nonfacial BSA	Randomization	1.5% BID	→ 1.5% BID → 1.5% QD → 0.5% QD → 0.15% QD	INCB018424 cream 1.5% BID	

Note: Subjects will be randomized equally to 1 of the 5 treatment groups and stratified by age ( $\leq$  30 or > 30 years). Note: Body surface area will be calculated using the palmar method, where the subject's palm is approximately equal to 0.5% BSA, and 1% BSA is approximately equal to a handprint (palm including 5 digits). a QD regimens will apply vehicle in the evening.

#### 3.1. Randomization

Approximately 150 subjects will be randomized to 1 of 4 dose strengths of INCB018424 cream (1.5% BID, 1.5% QD, 0.5% QD, or 0.15% QD) or vehicle cream in a 1:1:1:1:1 ratio, and stratified by age ( $\leq$  30 or > 30 years), with no more than 50% of the population being over 30 years of age. After completion of the Week 24 assessments, subjects randomized to vehicle will be randomized to 1 of the 3 higher active treatment groups while maintaining the blind. Subjects in the INCB018424 0.15% QD group who do not achieve a  $\geq$  25% improvement from baseline on F-VASI (nonresponders of F-VASI25) will be re-randomized to 1 of the 3 higher active treatment groups while maintaining the blind. Subjects randomized to INCB018424 0.15% QD who achieve a  $\geq$  25% improvement from baseline on F-VASI will remain on the same dose until Week 52. Subjects randomized to INCB018424 1.5% BID, 1.5% QD, and 0.5% QD will remain on the same dose until Week 52.

## 3.2. Control of Type I Error

For the primary endpoint and key secondary endpoints, the overall 2-sided Type I error is 0.05.

A graphical procedure with gatekeeping testing strategy for the primary and key secondary analyses will be implemented to control the overall Type I error rate.

[figure not shown]
<sup>b At Weeks 52 and 80, subjects with an F-PhGVA of clear (0) may stop application on the face, decrease to QD, or continue BID.

<sup>c Re-randomize to a higher dose if < 25% improvement in F-VASI score at Week 24. If  $\ge 25\%$  improvement in F-VASI, remain on the same dose until Week 52.

<sup>d Re-randomized to 1.5% BID, 1.5% QD, or 0.5% QD at Week 24 in a 1:1:1 ratio.

A family of 8 elementary hypotheses, corresponding to treatment comparisons between active treatment and vehicle groups, is evaluated in Figure 2, which is based on F-VASI50 and F-PhGVA at Week 24 and T-VASI50 at Week 52.

Figure 2: Illustration of the Statistical Treatment Comparisons

T = treatment group comparison.

#### 3.2.1. Primary Analysis

The primary endpoint is the proportion of subjects treated with INCB018424 cream who achieve a  $\geq 50\%$  improvement from baseline in F-VASI score (F-VASI50) at Week 24 compared with subjects treated with vehicle cream. The comparison of the primary endpoint will be performed for the superiority of either INCB018424 1.5% BID or INCB018424 1.5% QD versus vehicle (T11 and T21, respectively, in Figure 2) using the Bonferroni-Holm procedure at an overall 2-sided  $\alpha = 0.05$  level. The tests on the primary endpoint will be used as a gatekeeper for the 6 statistical tests on key secondary endpoints (see Figure 2).

#### 3.2.2. Secondary Analysis

The key secondary endpoint includes 6 comparisons as depicted in Figure 2.

- T31: INCB018424 0.5% QD is superior to vehicle at Week 24 on F-VASI50.
- T41: INCB018424 0.15% QD is superior to vehicle at Week 24 on F-VASI50.

- T12: INCB018424 1.5% BID is superior to vehicle at Week 24 on F-PhGVA response.
- T22: INCB018424 1.5% QD is superior to vehicle at Week 24 on F-PhGVA response.
- T13: INCB018424 1.5% BID is superior to 0.5% QD at Week 52 on T-VASI50.
- T23: INCB018424 1.5% QD is superior to 0.5% QD at Week 52 on T-VASI50.

The initial allocation of the overall significance level to Branch 1 (T12 and T22) and Branch 2 (T31 and T41) is 0.025, respectively. The weights of the level to be passed on if 1 hypothesis is rejected are specified in Figure 2.

#### **3.2.2.1.** Tests in Branch 1

The alternative hypotheses for T12 and T22 will be tested using the Bonferroni-Holm procedure at an overall 2-sided  $\alpha = 0.025$  level if the null hypotheses on primary endpoints are rejected.

If both T12 and T22 are rejected, T13 and T23 will be tested using Bonferroni-Holm procedure with overall 2-sided  $\alpha = 0.025$  level.

#### **3.2.2.2.** Tests in Branch 2

T31 (superiority of INCB018424 0.5% QD compared with vehicle) and T41 (superiority of INCB018424 0.15% QD compared with vehicle) will be tested sequentially at a 2-sided  $\alpha$  = 0.025 level if the null hypotheses on the primary endpoints are rejected.

## 3.3. Sample Size Considerations

In order to provide a large safety database and to provide adequate power for efficacy variables, the total sample size for the study is 150 subjects randomized in a 1:1:1:1:1 ratio (stratified by age) to INCB018424 1.5% BID, INCB018424 1.5% QD, INCB018424 0.5% QD, INCB018424 0.15% QD, or vehicle. The sample size selection is based on the assumed response rates of 55% for the INCB018424 1.5% cream BID group, 50% for the INCB018424 1.5% cream QD group, and 5% for the vehicle cream BID group. Using a 2-sided Bonferroni corrected  $\alpha$  of 0.025, 25 subjects per group will have a > 90% power to detect such a difference between each of the active treatment groups and the vehicle group based on Fisher's exact test due to small expected frequency of responders in the vehicle group. Assuming a 20% dropout rate during the first 24 weeks, approximately 150 subjects will need to be randomized.

#### 3.4. Schedule of Assessments

See Protocol Amendment 1 dated 17 MAY 2017 for a full description of all study procedures and assessment schedules for this study.

#### 4. DATA HANDLING DEFINITIONS AND CONVENTIONS

## 4.1. Scheduled Study Evaluations and Study Periods

Table 1: Definition of Day 1, Baseline, and Last Available Value

Study Period	Treatment Group*	Day 1	Baseline	Last Available Value
DB period	INCB018424 cream 1.5% BID 1.5% QD 0.5% QD 0.15% QD Vehicle BID	Date of first application or date of randomization for subjects randomized but not treated in the DB period.	The last nonmissing measurement obtained on or before the day of the first application.	The last nonmissing measurement obtained after the first application, and within 30 days after the last application in the DB period or before the first application in the extension period, whichever is earlier.
OL period	INCB018424 cream 1.5% BID	Date of first application date in DB period.	The last nonmissing measurement obtained on or before the day of the first application in DB period.	The last nonmissing measurement obtained after the first application and within 30 days after the last application.
	INCB018424 cream 1.5% QD 0.5% QD 0.15% QD Vehicle BID	Date of first application in OL period.	The last nonmissing measurement obtained on or before the day of the first application in the OL period.	The last nonmissing measurement obtained after the first application and within 30 days after the last application.

\* Treatment group initially assigned or actual treatment received during the DB period.

#### **4.1.1. Study Day**

Study Day 1 is used to calculate the study day for mapping scheduled visits. Study Day 1 is the date of the first application of INCB018424 cream or vehicle in the DB treatment period.

If a visit/reporting date is on or after Study Day 1, then the study day at the visit/reporting date will be calculated as

Study Day # = (Visit/Reporting Date - Study Day 1 date + 1).

If the visit/reporting date is before Study Day 1, then the study day at the visit/reporting date will be calculated as

Study Day # = (Visit/Reporting Date - Study Day 1 date).

A study day of -1 indicates 1 day before Study Day 1.

#### 4.2. Variable Definitions

#### 4.2.1. Age

Subject age will be calculated as the integer part of the number of years from date of birth to the date of signing the informed consent form, using the following formula:

Age = integer part of (date of informed consent – date of birth + 1) / 365.25

#### 4.2.2. Body Mass Index

BMI will be calculated as follows:

BMI  $(kg/m^2) = [weight (kg)] / [height (m)]^2$ 

#### 4.2.3. Prior and Concomitant Medication

Prior medication is defined as any nonstudy medication started before the first application of INCB018424 cream or vehicle cream.

Concomitant medication is defined as any nonstudy medication that is:

- Started before the date of first application of INCB018424 cream or vehicle cream and is ongoing throughout the study or ends on/after the date of first application of INCB018424 cream or vehicle cream.
- Started on/after the date of first application of INCB018424 cream or vehicle cream and is ongoing or ends during the course of study treatment.

A prior medication could also be classified as "both prior and concomitant medication" if the end date is on or after first application of INCB018424 cream or vehicle cream. In the listing, it will be indicated whether a medication is prior-only, concomitant-only, or both prior and concomitant

For the purposes of analysis, all medications will be considered concomitant medications unless the medications can unequivocally be defined as not concomitant.

#### 4.2.4. Handling of Missing and Incomplete Data

For response endpoints, all nonresponders, as well as all subjects who discontinue study treatment at any time before the timepoint of interest or discontinue from the study for any reason will be defined as nonresponders for NRI analysis.

For other endpoints, missing observations will be handled as detailed in the specific sections addressing each analysis.

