If a subject has vitiligo present on more than 20% of BSA, the application of study drug will be limited to $\leq 20\%$ of the subject's total BSA and areas treated at baseline should continue to receive treatment until the end of the double-blind period (Week 52) unless the subject meets criteria for stopping study drug because of an AE.

Reference Therapy, Dosage, and Mode of Administration: Vehicle cream is matching in appearance to INCB018424 cream and is to be applied in the same manner as INCB018424 cream.

Study Schedule/Procedures:

Study visits are as follows:

Screening: Up to 28 days before enrollment. Screening will begin at the time that the subject signs the informed consent and will continue until the date the subject is enrolled in the study (Day 1).

Vehicle-controlled, double-blind treatment: Subjects will have study visits on Day 1 and at Weeks 4, 8, 12, 18, and 24 for assessment of safety and efficacy.

Continued double-blind treatment: Subjects will have study visits at Weeks 28, 34, 40, 46, and 52 for assessment of safety and efficacy.

Open-label extension: Subjects will have visits at Weeks 56, 68, 80, 92, 104, 116, 128, 140, and 156 for assessment of safety and efficacy.

On the day of a visit, subjects should not apply the study drug at home and will apply the next dose of study drug from the new kit in the clinic. Subjects will be given a daily diary to record application times. Subjects will also be instructed to bring all study drug tubes with them to each visit so that compliance can be assessed.

Safety follow-up: Subjects will have follow-up assessments approximately 1, 3, and 6 months after the last dose of study drug to assess safety and efficacy. If prohibited treatment for vitiligo is started, then an earlier follow-up visit will be performed as a final, and thus end-of-study, visit.

Safety assessments:

At each scheduled study visit at the clinical site, targeted physical examinations, vital sign collection, laboratory assessments, collection of concomitant medications, and AE assessments will be performed.

Urinalysis and a 12-lead ECG will be performed at screening and end of treatment. All laboratory assessments will be performed using a central laboratory except for urine pregnancy tests. Toxicities will be monitored continuously and will be graded using the National Cancer Institute CTCAE v4.03 criteria.

Efficacy assessments:

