4.5. Overall Study Duration

The study begins when the first subject signs the ICF. The end of the study will occur when all subjects have discontinued study drug and have completed applicable follow-up assessments.

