|------------|---------|---------------|------------------------|--------------|--------------|---------------|---------------|---------------|
| | | Day -28 to -1 | Day 1 | Week 4 ± 3 d | Week 8 ± 3 d | Week 12 ± 3 d | Week 18 ± 7 d | Week 24 ± 7 d |
| | | | | | | | | |

^a Height and weight at screening only.

^b Serum FSH to be performed for all postmenopausal women only (defined by last menstrual period > 12 months before screening and confirmation by FSH in the postmenopausal range).

^c All women will have a serum pregnancy test conducted at the screening visit and urine pregnancy tests conducted at all other visits (including baseline).

Table 3: Schedule of Assessments During the Continued Double-Blind Period (Weeks 28 Through 52)

| Evaluation | Section | Double-Blind Extension Period | | | | | Follow-Up | |
|--|---------|-------------------------------|---------------------|---------------------|---------------------|-------------------------------|-------------------------------|----------------------------|
| | | Week 28 ± 7 Days | Week 34 ± 7 Days | Week 40 ± 7 Days | Week 46 ± 7 Days | Week 52 EOT/ET ± 7 Days | Months 1 and 3 ± 7 Days | Month 6 EOS ± 7 Days |
| Administrative procedures | | | | | | | | |
| Contact IRT | 7.2 | X | X | X | X | X | X | X |
| Prior/concomitant medications | 7.4 | X | X | X | X | X | X | X |
| Apply study drug | 5.2 | X | X | X | X | | | |
| Study drug and diary card dispensed | 7.10.1 | X | X | X | X | | | |
| Collect study drug tubes; collect and review diary cards | 5.3 | X | X | X | X | X | | |
| Assess compliance | 5.3 | X | X | X | X | X | | |
| Safety procedures/assessments | | | | | | | | |
| Comprehensive physical examination | 7.5.2.1 | | | | | X | | |
| Targeted physical examination | 7.5.2.2 | X | X | X | X | | X | X |
| Vital signs | 7.5.3 | X | X | X | X | X | X | X |
| Hematology and chemistry assessments | 7.5.5 | X | X | X | X | X | X | X |
| Urinalysis ^a | 7.5.5.3 | | | | | X | | |
| Pregnancy test ^b | 7.5.5.4 | X | X | X | X | X | X | X |
| 12-lead ECG ^a | 7.5.4 | | | | | X | | |
| Assess AEs | 7.5.1 | X | X | X | X | X | X | X |
| Efficacy and other assessments | | | | | | | | |
| VASI (face and total body) | 7.6.1 | X | X | X | X | X | X | X |
| BSA (face and total body) | 7.6.2 | X | X | X | X | X | X | X |
| VETF | 7.6.3 | X | X | X | X | X | | |
| | | | | | | | | |
| Physician - PhGVA (face and total body) | 7.6.4 | | | X | | X | | X |

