6.4. Follow-Up

Subjects will have follow-up assessments 1, 3, and 6 months after the last application of study drug. Although subjects will be asked not to apply any other medications for vitiligo during the follow-up period, if prohibited treatment for vitiligo is started, then an earlier follow-up visit may be performed. A final EOS visit should be performed, ideally no earlier than 30 days after the last dose of study drug. Adverse events and SAEs must be reported up until at least 30 days after the last dose of study drug, the date of the follow-up visit, or until toxicities resolve, return to baseline, or are deemed irreversible, whichever is longest. Reasonable efforts should be made to

have the subject return for the follow-up visits and report any AEs that may occur during this phase.

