#### 7. EFFICACY

Appendix A provides a list of data displays.

#### 7.1. General Considerations

For continuous measurements, summary statistics will include sample size, mean, median, standard deviation, standard error of the mean, minimum, and maximum. For all continuous variables, both the actual value and change and/or percentage from baseline (if available) will be analyzed.

For categorical measurements, summary statistics will include sample size, frequency, and percentages.

All by-visit analyses will include the follow-up period if the data are available.

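### The nonresponder rule is not limited to on-treatment visits, so early stoppers are scored as failures at post-treatment follow-up whatever is observed there

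*SAP*

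**What the plan says.** SAP 4.2.4 states the rule in general terms. On any response endpoint, the subjects scored as failures in the NRI analysis include "all subjects who discontinue study treatment at any time before the timepoint of interest". Leaving the study, whatever the cause, has the same effect. Only endpoints other than response endpoints are left to the individual analysis sections.

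SAP 7.1 then says: "All by-visit analyses will include the follow-up period if the data are available".

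The Protocol synopsis gives the timing and purpose of those visits: "Subjects will have follow-up assessments approximately 1, 3, and 6 months after the last dose of study drug to assess safety and efficacy". Protocol Tables 3 and 4 schedule VASI (face and total body) at Months 1, 3 and 6 of follow-up. They schedule PhGVA at Month 6 only.

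The SAP is dated June 2017 and was written against Protocol Amendment 1. SAP 2.1 extends it to later amendments unless it is superseded, and SAP 10 lists no later version. It therefore also governs the six-month follow-up of Protocol Version 3.

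**The concern.** A nonresponder rule makes sense at a visit where the subject was meant to be on treatment: stopping early counts as failure of the treatment strategy. A follow-up visit asks something else, namely whether pigment persists once the cream is stopped. Every subject seen there is off drug by design, so an earlier stop is no reason to discard the observation.

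The protocol asks sites to collect these data from early stoppers. Section 6.3 has them encouraged to return for follow-up, and section 5.5.2 lets a subject give up treatment yet stay on for safety and efficacy assessment. The rationale for Amendment 3, which lengthened both the open-label and the follow-up periods, includes maintenance of response. If the rule in SAP 4.2.4 is applied at these visits, VASI50 results gathered partly for that purpose are overwritten. If early stopping differs between arms, the distortion differs between arms too.

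**Working it through.** The plan states no figure for response at follow-up, so there is none to reproduce. The check is a reading of the sections together, followed by a simple illustration.

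**Step 1: which rule governs follow-up response.** SAP 7.4.2 lists F-VASI50, T-VASI50 and PhGVA clear or almost clear among the by-visit categorical summaries. It names no rule for missing data or discontinuation. SAP 7.1 takes by-visit analyses into follow-up. The only visible rule for scoring a response endpoint is then SAP 4.2.4, which has no restriction by visit type.

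**Step 2: who is caught by it.** SAP 6.2 counts subjects who completed a treatment period separately from those who discontinued with a primary reason. The Table 3 footnote and Protocol 7.5.4 and 7.5.5.3 likewise distinguish reaching Week 52 or Week 156 from stopping treatment. On that usage:

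| Subject | F-VASI50, T-VASI50 at Months 1, 3, 6 | PhGVA response at Month 6 |
|---|---|---|
| Stopped treatment early | Failure by rule | Failure by rule |
| Completed planned treatment | As observed | As observed |

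PhGVA is not scheduled at Months 1 and 3, so no scheduled observation is overridden there.

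**Step 3: size.** Let d be the share of early stoppers in the follow-up denominator, and let r_c and r_e be the observed response rates in completers and early stoppers.

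- Observed rate = (1 − d) × r_c + d × r_e
- Rate under the rule = (1 − d) × r_c
- Shortfall = d × r_e

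Inputs: d = 20%, borrowed from the dropout assumption in SAP 3.3. That assumption covers the first 24 weeks and is not a forecast for follow-up. All early stoppers are taken to be in the denominator. The documents give no follow-up response rate, so r_c = r_e = r is assumed at three values. The middle value, 55%, equals the Week 24 rate assumed in SAP 3.3 for 1.5% BID.

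| Observed r | Under the rule, r × (1 − 0.20) | Shortfall |
|---|---|---|
| 30% | 24% | 6 points |
| 55% | 44% | 11 points |
| 80% | 64% | 16 points |

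The shortfall depends on how early stoppers actually fare. With r_c = 55% and r_e = 0, the observed rate is 0.80 × 55% = 44%, and the rule changes nothing. So at d = 20% and r_c = 55%, the shortfall runs from 0 to 11 points as r_e goes from 0 to 55%.

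**The case against.** The best reply is that applying the rule at follow-up is an inference. SAP 4.2.4 sits under missing-data handling and defines nonresponders for the NRI analysis. The visible text invokes NRI by name only for the primary and key secondary endpoints at Weeks 24 and 52 (SAP 7.3.1 and 7.4.1). By-visit summaries are descriptive, and the data-availability proviso in SAP 7.1 can be read as observed-case language. The response tables listed in Appendix A run to Week 52 or cover the open-label period, and none is titled for follow-up. Parts of the SAP contents list around section 7.5 and after 7.6 are blanked, so a maintenance analysis may exist that cannot be seen here. Finally, the by-visit secondary response endpoints are defined over the treatment periods.

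Much of this stands, and it limits the point to a minor one. It does not remove it. The rule in SAP 4.2.4 is worded for response endpoints at large. The proviso in SAP 7.1 decides whether follow-up is included, not how a response is scored. Appendix A describes its own lists as guidance. Two programmers could reasonably produce different follow-up tables from this text.

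A reader might go further and infer that response would be zero in every arm at every follow-up visit, because all subjects are off drug by then and Protocol 4.5 ends the study when "all subjects have discontinued study drug and have completed applicable follow-up assessments", a phrase that takes in completers. The documents do not support that reading. Protocol 4.5 defines the end of the study and is not an analysis rule. Where the documents classify subjects, they keep completion and discontinuation apart.

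**Conclusion.** The point holds in limited form and is minor. On the visible text, early stoppers are failures by rule at follow-up while completers keep their observed values, so the follow-up response rate does not measure off-treatment maintenance. With 20% early stoppers all in the denominator and equal response in both groups, an observed 55% is reported as 44%. This illustration rests on assumed inputs. The actual shortfall is the share of early stoppers times their own observed response rate, and the documents give neither. Under Protocol 5.5.2, permanent discontinuation leads to withdrawal from the study, with only reasonable efforts to bring the subject back, so how many early stoppers are actually assessed is also unknown.

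Not affected: the Week 24 and Week 52 confirmatory tests, which concern on-treatment timepoints, and the by-visit changes in VASI and BSA, to which the rule does not apply. For that reason, a reader should not infer that the plan has no way to show durability. The gap concerns the response endpoints only.

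**What to change.** Amend SAP 4.2.4 so that the nonresponder rule applies to scheduled on-treatment visits only (double-blind to Week 52, and open-label visits), and state that completing planned treatment is not discontinuation.

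For follow-up visits:

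- Summarize observed F-VASI50 and T-VASI50, and PhGVA response at Month 6, by time since the last dose.
- Present completers and early stoppers separately.
- Among responders at end of treatment, give the proportion who keep response at each follow-up visit, with the number assessed.

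If a redacted section already provides this, a cross-reference from SAP 4.2.4 and 7.1 is enough.

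The cost is a few sentences and a small set of descriptive tables, with no new data. The drawback is that observed-case rates depend on who returns, so the numbers expected and seen should appear beside each rate.
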